11.1.2. Protocol-Defined AESI

Protocol-defined AESIs are defined in Section [9.5.12](#).

Note, for Suicidality (C-SSRS) only, a subject must have at least one pre-treatment C-SSRS assessment (screening and/or baseline) and at least one on-treatment C-SSRS assessment (post-baseline) to be included in the summaries.

Percentages

For each of the AESIs a summary of the number and percentage of subjects experiencing at least one event will be provided for belimumab and placebo as well as the difference in the percentage of subjects (and 95% CI) between the belimumab and placebo groups using the same methodology as for mortality.

Subject Incidence Rate

The incidence rate for each AESI per 100 subject years will be provided for belimumab and placebo groups as well as the difference between placebo and belimumab (and 95% CI) using the same methodology as for mortality.

Event Incidence Rate

The number of events and event rate for each AESI, except Suicidality (C-SSRS), per 100 subject years will be provided for belimumab and placebo groups.

11.1.3. SAEs

SAEs will be presented using descriptive statistics.

A summary of the number and percentage of subjects with SAEs reported during the on-treatment and on-study (to Week 52) periods will be provided along with the number of events. Subject incidence rates will also be provided at the SOC level only (see Section [9.5.14](#) for derivation) for on-treatment and on-study periods.

See Section [11.2.1](#) for further details of SAE summaries and Section [11.2.2](#) for a description of the SAE listings.

11.2. Other Safety Summaries

11.2.1. AESI and SAEs

This section describes additional summaries to be generated for all safety data in the AE dataset. These data will be referred to as AESIs and SAEs throughout this section but could include out of scope AEs if entered by sites. For the AESI analysis/groupings as per the Belimumab PSAP definitions, see Section [11.2.4](#) (and Section [9.2](#) for AESI adjudication details).

For the following summaries, only treatment-emergent AESIs and SAEs will be summarized, unless otherwise stated (see Section 9.5.13 for definitions of Treatment Emergent and derivation of AE duration).

All treatment-emergent AESIs and SAEs will be summarized for the On-Treatment and On-Study (to Week 52) periods, unless otherwise specified in the list of displays.

All AESIs and SAEs will be classified using the Medical Dictionary for Regulatory Activities (MedDRA) dictionary, and grouped by SOC and preferred term (PT), unless otherwise stated.

The investigator will evaluate all AESIs and SAEs with respect to seriousness, severity, and causality. The severity of an AESI or SAE is to be evaluated according to the Adverse Event and Laboratory Value Severity Grade Tables in Protocol Appendix 8, if a grade is defined for the AE of interest.

An overall summary of AESIs and SAEs will be presented showing the number and percent of subjects with at least one: AESI or SAE, Study Agent related AESI or SAE, serious AE (SAE), severe AESI or SAE, AESI or SAE resulting in premature study agent discontinuation, AESI or SAE resulting in study withdrawal, AESI or SAE resulting in premature study agent discontinuation and/or study withdrawal, deaths (timing based on fatal SAE start date) and deaths (timing based on fatal SAE end date i.e. date of death). This summary will be presented for the On-Treatment and On-Study periods.

The number and percentage of subjects experiencing an AESI or SAE and the total number of AESIs and SAEs will be summarized for AE categories and treatment periods as shown in Table 1.

A listing of subject numbers for each AESI or SAE will also be produced. AESIs and SAEs will be grouped and sorted by SOC and PT. A listing of all AESIs and SAEs and study agent related AESIs and SAEs will be presented, including duration and study day of onset/resolution.

Table 1 AESIs and SAEs Displays

Category	On-Treatment Period	On-Study (to Week 52) Period
All AESIs and SAEs	by SOC by SOC and PT by PT only	by SOC and PT
AESIs and SAEs by Severity	by SOC and PT	
Serious AEs	by SOC by SOC and PT by PT	by SOC and PT
Study Agent Related AESIs and SAEs	by SOC by SOC and PT by PT only	
Study Agent Related AESIs and SAEs by Severity	by SOC and PT	

Category	On-Treatment Period	On-Study (to Week 52) Period
AESIs and SAEs Leading to Premature Discontinuation of Study Agent	by SOC and PT by PT	by SOC and PT
AESIs and SAEs Leading to Withdrawal from Study	by SOC and PT	by SOC and PT
Common Non-Serious AESI $\geq 1\%$	by SOC and PT	
Non-serious Study Agent Related AESI	by PT	
Study Agent Related SAEs	by SOC and PT by PT	
Fatal SAEs (assigned to period based on SAE start date)	by SOC and PT by PT	by SOC and PT
Study Agent Related Fatal SAEs (assigned to period based on SAE start date)	by SOC and PT	
AESIs and SAEs by Age group	by SOC and PT	
AESIs and SAEs by Gender	by SOC and PT	
AESIs and SAEs by Race	by SOC and PT	
AESIs and SAEs by Region	by SOC and PT	
AESIs and SAEs by Complement Levels and Anti-dsDNA	by SOC and PT	

The tabular summary for each category of AESIs and SAEs listed above will include the number of events, number of subjects who reported at least one event, and percentage of subjects who reported at least one AESI or SAE (incidence) by treatment group for each SOC (where applicable), each PT, and overall. By default, adverse events will be sorted by MedDRA SOCs, in descending order from the SOC with the highest total incidence (i.e., summed across all treatment groups) for any adverse event within the class, to the SOC with the lowest total incidence. If the total incidence for any two or more adverse events is equal, the events will be presented in alphabetical order. Only SOCs with observed AE PTs will be presented. Repeat sort order for MedDRA PTs within each SOC.

Common AESIs and SAEs will be defined as $\geq 1\%$ in either treatment group.

For disclosure, an additional summary of SAEs by SOC and PT will be produced in the format required for the on-treatment period. The table will include the number and percentage of subjects with an SAE along with the number of SAEs, drug-related SAEs, fatal SAEs and drug-related fatal SAEs.

A summary of AESIs and SAEs by SOC, PT and severity will be provided by treatment group. For this display, the number and percentage of subjects will be summarized as mild, moderate or severe based on the maximum severity observed across all PTs within the SOC for a given subject.

The hierarchical relationship between MedDRA SOCs, PTs, and verbatim text will be listed for all AESIs and SAEs.

A listing that displays which subjects reported each AESI or SAE will also be produced. AESIs and SAEs will be grouped and sorted by SOC and PT.

A listing of all AESIs and SAEs and study agent related AESIs and SAEs will be presented, including duration and study day of onset/resolution.

A listing of SAEs and AESIs that are recorded between withdrawal of consent and Week 52 Follow-Up, excluding mortality and malignancy, will be produced. The intent is to capture events that were not included in summaries for the on-study period as the protocol did not specify to collect them.

11.2.2. Deaths and Serious Adverse Events

In addition to the tabular summaries of AESIs and SAEs described in Section 11.2.1, listings for all SAEs, all fatal SAEs (deaths) and all non-fatal SAEs will be produced. A listing of reasons for considering an AE as an SAE will be provided. The categorization of the cause of death will be adjudicated by GSK (see Section 9.2).

A summary of deaths (fatal SAEs) by category and preferred term will be produced based on the start date of the fatal SAE (to determine whether the event occurred during the relevant study period). A separate summary will be produced of deaths by category and preferred term based on end date of fatal SAE (i.e. using date of death to determine whether the event occurred during the relevant study period). Both summaries will be for the on-treatment period.

Survival status will also be summarized at Week 52, based on information collected on the Week 52 Survival form, for all subjects in the As-Treated population. The number and percentage of subjects will be summarized for each of the following categories:

- Alive
- All Deaths (based on date of death)
 - Deaths on Treatment (during the on-treatment period)
 - Deaths Post-Treatment (after the on-treatment period)
- Unknown
 - Lost to Follow-Up
 - Unattainable

A listing of survival status at Week 52 will also be presented.

11.2.3. AESIs and SAEs Leading to Discontinuation of Investigational Product or Withdrawal from Study

In addition to the tabular summaries described in Section 11.2.1, the following listings will also be produced:

- all AESIs and SAEs leading to premature discontinuation of study agent.
- all AESIs and SAEs leading to withdrawal from the study (i.e., withdrawal of consent).

Note that non-serious AEs leading to withdrawal that are not protocol-defined AESI are not collected in the database.

11.2.4. PSAP-Defined Adverse Events of Special Interest

The PSAP has been developed to include AESI summaries for consistent reporting across belimumab studies which will be included here in addition to the primary summary of overall AESI rates described in Section 11.1.2 of this RAP.

Categorizations for the AESIs from the PSAP are defined [Appendix 6: PSAP Sections for AESI Reporting](#) and reporting of AESIs for these analyses is defined below.

An overall summary of AESI will be presented. Selected categories of AESI will be presented separately by PT. Infection AESIs will also be presented by PT for infections leading to discontinuation of study agent. The number and percentage of subjects with at least one occurrence and the number of events of the following AESI will be provided.

- Malignant Neoplasms
 - Malignancies Excluding non-melanoma skin cancer (NMSC) [see Section 9.5.12, protocol defined AESI]
 - Malignancies Including NMSC
 - Solid Tumour
 - Hematologic
 - Skin (All)
 - NMSC [see Section 9.5.12, protocol defined AESI]
 - Excluding NMSC
 - Tumours of unspecified malignancy adjudicated as malignant per GSK adjudication
- Post-Infusion Systemic Reactions
 - Post-Infusion Systemic Reactions per Anaphylactic Reaction Customized MedDRA Query (CMQ) narrow search (on the day of the infusion or within 3 days after the infusion)
 - Serious Post-Infusion Systemic Reactions per Anaphylactic Reaction Customized MedDRA Query (CMQ) narrow search (on the day of the infusion or within 3 days after the infusion)

- Post-Infusion Systemic Reactions per Anaphylactic Reaction CMQ broad search (on the day of the infusion or within 3 days after the infusion)
 - Serious Post-Infusion Systemic Reactions per Anaphylactic Reaction CMQ broad search (on the day of the infusion or within 3 days after the infusion) [see Section 9.5.12, protocol defined AESI]
 - Post-Infusion Systemic Reactions per Anaphylactic Reaction CMQ algorithmic search (on the day of the infusion or within 3 days after the infusion)
 - Serious Post-Infusion Systemic Reactions per Anaphylactic Reaction CMQ algorithmic search (on the day of the infusion or within 3 days after the infusion)
 - Serious Anaphylaxis per Sampson Criteria
 - Serious Acute Post-Infusion Systemic Reactions/Hypersensitivity per GSK adjudication
 - Serious Acute Post-Infusion Systemic Reactions Excluding Hypersensitivity per GSK adjudication
 - Serious Acute Hypersensitivity Reactions per GSK adjudication
 - Serious Delayed Acute Hypersensitivity Reactions per GSK adjudication
 - Serious Delayed Non-Acute Hypersensitivity Reactions per GSK adjudication
- All Infections of Special Interest [see Section 9.5.12, protocol defined AESI]
 - Serious Infections of Special Interest
 - All opportunistic infections per GSK adjudication
 - Serious opportunistic infections per GSK adjudication
 - Opportunistic infections per GSK adjudication excluding Tuberculosis and Herpes Zoster
 - Serious opportunistic infections per GSK adjudication excluding Tuberculosis and Herpes Zoster
 - Active Tuberculosis
 - Non-Serious Active Tuberculosis
 - Serious Active Tuberculosis
 - Non-Opportunistic
 - Serious Non-Opportunistic
 - Opportunistic
 - Serious Opportunistic
 - Herpes Zoster
 - Serious Herpes Zoster
 - Non-Opportunistic
 - Serious Non-Opportunistic
 - Opportunistic
 - Serious Opportunistic
 - Recurrent

- Serious Recurrent
 - Disseminated
 - Serious Disseminated
- Sepsis
 - Serious Sepsis
- Depression/suicide/self-injury
 - Depression (Inc. mood disorders and anxiety)
 - Serious Depression (Inc. mood disorders and anxiety) [see Section 9.5.12, protocol defined AESI]
 -
 - Suicide/self-injury
 - Serious Suicide/self-injury
 - Serious Suicide/Self-injury per GSK Adjudication
 - Suicidal behavior per GSK Adjudication
 - Completed Suicide per GSK Adjudication
 - Suicidal Ideation per GSK Adjudication
 - Self-injurious Behavior Without Suicidal Intent per GSK Adjudication
- Deaths (using start date of fatal SAE to determine whether event occurred during the relevant study period)
- Deaths (using end date of fatal SAE i.e. date of death to determine whether event occurred during the relevant study period)

A listing of all PSAP-defined AESIs will be produced.

11.2.4.1. Post-infusion Systemic Reactions

Summaries of post-infusion systemic reactions will be presented by the first six infusions and PT for the following categories:

- Serious Post-Infusion Systemic Reactions per Anaphylactic Reaction CMQ broad search (on the day of the infusion or within 3 days after the infusion)
- Serious Acute Post-Infusion Systemic Reactions per GSK adjudication
- Serious Delayed Acute Post-Infusion Systemic Reactions per GSK adjudication
- Serious Delayed Non-Acute Post-Infusion Systemic Reactions per GSK adjudication

11.2.5. Columbia-Suicide Severity Rating Scale (C-SSRS)

The definition of treatment-emergent with respect to C-SSRS (suicidal ideation and/or behavior) is given in Section 9.5.15.

Suicidality assessments are completed at every visit. Assessments are done using the C-SSRS. If a “yes” response is given to any suicidal behavior or a “yes” response to suicidal ideation questions with category 3, 4 or 5 on the C-SSRS, the investigator will be

prompted to complete the Possible Suicidality Related Questionnaire (PSRQ). A listing of the PSRQ will be presented.

Listings will be generated for the following:

- Suicidal ideation and behavior data for subjects who have any suicidal ideation or behavior recorded at any point on the study (including screening or baseline).
- Behavior details for subjects who have any suicidal behavior recorded at any point on the study (including screening or baseline)
- The most severe suicidal ideation details for subjects who have any suicidal ideation recorded at any point on the study (including screening or baseline).

11.2.5.1. C-SSRS Suicidal Ideation or Behavior

The number and percentage of subjects with suicidal ideation or behavior at any time during the on-treatment and on-study (to Week 52) periods will be presented. For suicidal ideation, the maximum ideation score (1-5) at any time during the relevant period will be presented. For suicidal behavior, all behaviors (6-10) present at any time during the relevant period will be presented. This will be regardless of whether the subject had pre-treatment history (up to and including baseline [see Section 9.5.1 for baseline definition]). The categories of suicidal ideation and behavior are presented in increasing order of severity from 1 to 5, and 6-10 respectively.

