¹ A urine pregnancy test is required for women of child bearing potential. The results of urine pregnancy test must be available prior to dosing.

GlaxoSmithKline group of companies

- 2 The weight at the current visit should be used to calculate dose. Refer to Section 5.2 for further information.
- 3 Suicidality is to be assessed prior to study agent infusion using the "Since Last Visit" C-SSRS (Appendix 5).
- 4 Subjects should remain under clinical supervision for 3 hours after completion of the first 2 study agent infusions. Should symptoms of acute hypersensitivity occur, an extended period of monitoring may be appropriate, based on clinical judgment.
- 5 All SAEs will be recorded. These data will be used to analyze serious infections and selected serious psychiatric events.
- 6 Guidelines for opportunistic infections and other infections of interest are provided in Appendix 2.
- 7 A hospitalization is an inpatient admission for any length of time. An admission for administration of study agent, for routine or planned clinical procedures, or for "social" reasons (not the result of any adverse change in the subject's condition) should not be recorded as a hospitalization.
- 8 Pharmacogenetic sampling informed consent must be obtained prior to any blood being taken for PGx research. Sample should be drawn prior to dosing on Day 0. However, the sample may be collected at any time during the study.
- 9 Refer to Appendix 3. SLICC/ACR Damage Index is only performed at Screening and Week 52 (but not earlier if a subject discontinues study agent).
- 10 If a subject withdraws consent to participate in the first year monthly study visits, it is requested that the site attempt to obtain consent to contact the subject at Week 52 and annually for Years 2 through 5 (Week 260) to assess mortality and malignancy (including NMSC).
- 11 Following the study, all subjects will be contacted annually through Year 5 (Week 260) to assess mortality and malignancy (including NMSC).

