On-Treatment	
All data:
 
 • Study Treatment Start Date ≤ Date ≤ minimum (Date of Death, Study Treatment Stop Date + 28 days)

Note: After study withdrawal or last exposure plus 28 days (whichever occurs later) if AESIs and SAEs are recorded, other than mortality and malignancy, these will not be included in the on-study period. See Section 11.2.1 for further detail on how these events will be handled.

Note: For mortality, date of death will be derived as the end date of the SAE with fatal outcome.

Note: Each study treatment infusion should have a start date and end date recorded, but in some cases only one variable is completed. The study treatment stop date is the date of the final study treatment infusion (taken as the first non-missing date of the final study treatment infusion start or end date).

Note: Only dates will be used to identify start and end of treatment (times will not be considered).

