9.5. Derived and Transformed Data

9.5.1. Baseline

The protocol specifies Day 0 as Baseline/Treatment Start date, but the CDISC standard is to refer to the Baseline/Treatment Start date as Day 1; therefore Baseline/Treatment Start date will be referenced as Day 1 in this document. A table indicating the target study day for each planned visit is in Section 9.5.3.

The baseline value of a variable is defined as the last available value measured prior to dosing on or before the date of first dose (Day 1), unless otherwise specified.

If the last available value occurs on Day 1 but the time of the assessment is not collected, then the assessment will be assumed to be prior to dosing. Noted exceptions to this rule are concomitant medications and AEs; these will be considered as being concomitant and treatment-emergent, respectively, if the start date occurs on the first day of dosing.

However, if time is available for an AE or concomitant medication and the end time is earlier than the start time of first dose of IP, the AE or concomitant medication will not be considered as treatment-emergent or concomitant, respectively.

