11.2.5.2. C-SSRS Suicidal Ideation or Behavior Relative to Pre-Treatment

The number and percentage of subjects with treatment-emergent suicidal ideation or behavior -post-baseline will be presented during the on-treatment and on-study (to Week 52) periods (see Section 9.5.15).

A subject must have at least one pre-treatment C-SSRS assessment (screening and/or baseline) and at least one on-treatment C-SSRS assessment (post-baseline) to be included in this display.

A subject may have treatment emergent suicidal ideation and/or behavior.

The following categories will be presented:

- The number (%) of subjects with any treatment emergent suicidal ideation (1-5)
 - The number (%) of subjects with any treatment emergent more severe suicidal ideation (4-5)
- The number (%) of subjects with any treatment emergent suicidal behavior (6-10)
- The number (%) of subjects with any treatment emergent suicidal ideation (1-5) or suicidal behavior (6-10)

Note: treatment emergent suicidality can only be assessed in subjects with a pre-treatment maximum ideation score of 4 or lower (as subjects with a pre-treatment ideation score of 5 have no potential to worsen on the 1-5 ideation scale)

In addition, a shift table showing the maximum pre-treatment ideation score versus the maximum post-treatment ideation score will be produced for the on-treatment and on-study periods. The maximum pre-treatment behavior score versus the maximum post-treatment behavior score will also be presented in the summary table. These summaries will be provided post Statistical Analysis Complete (SAC).

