11.2.5.3. C-SSRS Shift Changes in Categories from Pre-Treatment to On-Treatment

A summary of the shift from maximum pre-treatment C-SSRS category to maximum on-treatment and on-study (to Week 52) category will be produced.

The pre-treatment period for ideation is based on the lifetime, current and baseline history. For behavior, it is based on the lifetime and baseline history. A subject must have at least one pre-treatment assessment and at least one on-study assessment to be included in this display.

The table will display the number and percentage of subjects within the specific shift categories: No suicidal ideation or behavior, suicidal ideation, and suicidal behavior.

Each subject will appear in the table only once. For the purposes of this table only, a subject with both suicidal ideation and suicidal behavior in any period (pre-treatment/on-treatment/on-study) will appear in the category of suicidal behavior only.

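### The Week 52 SAP requires an on-treatment C-SSRS even for on-study suicidality results, and its period and baseline rules conflict on the Day 1 C-SSRS

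*SAP*

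**What the plan says.** All section numbers are from the Week 52 SAP unless the protocol is named.

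**Who is included.** Section 9.5.15 assesses treatment emergence separately for the on-treatment and on-study periods. Section 9.1.1 describes the on-study period as covering data on and off treatment to Week 52. The inclusion rules are:

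- 11.2.5.2, which presents both periods, requires "at least one on-treatment C-SSRS assessment (post-baseline) to be included in this display". Sections 9.5.15 and 11.1.2 (the protocol-defined AESI) carry the same on-treatment condition.
- 11.2.5.3, also for both periods, says: "A subject must have at least one pre-treatment assessment and at least one on-study assessment to be included in this display".
- 11.2.5.1 has no inclusion rule.

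**Which side of dosing Day 1 falls on.** Protocol Table 6-1 schedules the since-last-visit C-SSRS from Day 0 onwards, and its footnote 3 says "Suicidality is to be assessed prior to study agent infusion". Section 9.1.1 defines on-treatment, for all data, as "Study Treatment Start Date ≤ Date ≤ minimum (Date of Death, Study Treatment Stop Date + 28 days", and adds "Only dates will be used to identify start and end of treatment (times will not be considered". On-study starts on the same date. Pre-treatment is strictly before it.

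Section 9.5.1 says of a last value that falls on Day 1: "but the time of the assessment is not collected, then the assessment will be assumed to be prior to dosing". Only AEs and concomitant medications are excepted. Section 9.5.15 places baseline in the C-SSRS pre-treatment reference period, and 10.3 tabulates the Day 1 C-SSRS with the baseline characteristics. Section 11.2.5.1 counts subjects "with suicidal ideation or behavior at any time during the on-treatment and on-study (to Week 52) periods will be presented", without limiting the count to post-baseline assessments.

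**The concern.** The on-study results exist to add what happens after study agent is stopped. An entry condition that can be met only on treatment works against that purpose. If a subject's only post-baseline C-SSRS is off treatment and shows new ideation, the on-study AESI loses both the subject and the event. That AESI is in Table 2.06, which Section 16.3 lists as a headline result, and suicidality is one of the risks the protocol's rationale (Section 1.3) names as a focus of the trial.

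On Day 1, one record belongs to two opposing periods, depending on which section is followed. Read literally by date:

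- ideation reported only before the first infusion counts in 11.2.5.1;
- the same record can set both sides of the shift tables in 11.2.5.2 and 11.2.5.3;
- Day 1 alone satisfies the on-study part of the 11.2.5.3 inclusion rule, so a subject never assessed after dosing could enter that table.

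**Working it through.** The plan states no figure on this point, so there is none to reproduce. The checks are date logic, visit windows and a short algebraic argument.

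**1. Who can be dropped by the inclusion rule.** Inputs: on-treatment ends 28 days after the last infusion date (9.1.1). Target study days are 15, 29 and 57 for Weeks 2, 4 and 8 (9.5.3). Windows are ±3 days for Weeks 2 and 4 and ±7 days from Week 8 (protocol 6.3).

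For a single infusion on study Day 1, on-treatment ends on Day 1 + 28 = Day 29.

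| Visit | Window (study days) | Part inside on-treatment |
|---|---|---|
| Week 2 | 12–18 | all |
| Week 4 | 26–32 | Days 26–29 |
| Week 8 | 50–64 | none |

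A subject with a second infusion is due a C-SSRS before it, and that assessment is both post-baseline and on-treatment. The subjects lost are therefore essentially those with one infusion, no C-SSRS by Day 29 and a later one, plus any who missed every C-SSRS in their window. Protocol 6.5 keeps subjects who stop study agent on the visit schedule to Week 52, so such later assessments can exist.

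**2. Day 1 by date.** Start date ≤ Day 1 is true, so Day 1 is on-treatment and on-study. Day 1 < start date is false, so it is not pre-treatment. Sections 9.5.1 and 9.5.15 nevertheless make it baseline and part of the pre-treatment reference.

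**3. Effect on the treatment-emergent flag.** Let s, d and p be the screening, Day 1 and later maximum scores.

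- Day 1 as baseline only: emergent if p > max(s, d).
- Day 1 on both sides: emergent if max(p, d) > max(s, d).

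If p > d the two conditions are identical. If p ≤ d the second becomes d > max(s, d), which is impossible, and the first fails as well. Enumerating ideation scores 0–5 for s, d and p gives 0 disagreements in 6 × 6 × 6 = 216 combinations. The algebra holds equally for the behavior scale.

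**4. Effect on the 11.2.5.1 counts (assumed values only).** Assume 2,000 per arm, later ideation in 2% of one arm and 3% of the other, and Day 1 ideation with probability b in both arms, independent of later ideation. Extra subjects in an arm with later rate r are 2,000 × b × (1 − r).

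- b = 0.5%: in the 2% arm, 2,000 × 0.005 × 0.98 ≈ 10 extra. The rates become 2.49% and 3.485%: difference 0.995 points, ratio 1.40.
- b = 3%: in the 2% arm, 2,000 × 0.03 × 0.98 ≈ 59 extra. The rates become 4.94% and 5.91%: difference 0.97 points, ratio 1.20.

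Without Day 1 the difference is 1.00 point and the ratio 1.50. If Day 1 and later ideation go together, fewer subjects are added.

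**The case against.** **On inclusion.** The rules gloss on-treatment as post-baseline, so the word may have been used loosely, in which case nobody is dropped. That is possible, but on-treatment is a defined period in 9.1.1, 9.5.15 itself distinguishes it from on-study, and 11.2.5.3 uses on-study for the corresponding rule. As written, the condition excludes. A reader might infer that the on-study display loses early discontinuers as a group. It does not: the Week 2 window lies wholly inside the on-treatment period even after one infusion. Nor does the exclusion arise in 11.2.5.1, which has no such rule.

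**On Day 1.** A reader might infer that pre-dose ideation is definitely counted as on-treatment. The documents do not settle that. Sections 9.5.1, 9.5.15 and 10.3 treat Day 1 as baseline, the post-baseline gloss points the same way, and 11.2.5.1 itself places baseline in the pre-treatment history. The 11.2.5.2 shift table speaks of post-treatment scores, which a pre-infusion record does not naturally supply. This stands: it is a conflict between rules, and the display shells and the standards documentation that 9.5.15 cites are not available to show how it was resolved. It does not close the gap, because 11.2.5.1 mentions earlier history only to say that subjects count regardless of it, and no sentence removes the Day 1 record.

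Two further inferences fail. Dilution of the treatment contrast has no planned target, since 11.2.5.1 gives counts and percentages only. Concealed improvement is not a fair charge, since the pre-treatment side of the shift tables is a maximum that includes lifetime history and so does not measure change from Day 1.

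**Conclusion.** The inclusion rule is wrong as written for the on-study suicidality results and conflicts with both the on-study definition and 11.2.5.3. Few subjects should be affected. How many cannot be derived from the documents, and the estimate of few assumes that the scheduled C-SSRS were mostly done.

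The Day 1 point is a secondary, unresolved conflict that touches the descriptive counts in 11.2.5.1, the shift tables in 11.2.5.2 and 11.2.5.3, and the 11.2.5.3 inclusion rule. It leaves the treatment-emergent suicidality flag unchanged. Its size cannot be estimated, because no Day 1 ideation rate is given; the figures in step 4 only illustrate assumed values. Both points are minor clarifications and do not threaten the trial's main safety conclusions.

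**What to change.** - In 9.5.15, 11.1.2 and 11.2.5.2, require at least one pre-treatment C-SSRS and at least one post-baseline C-SSRS in the period being summarised, on-treatment or on-study as applicable.
- In 11.2.5.1, and in the shift tables of 11.2.5.2 and 11.2.5.3, state that the on-treatment and on-study summaries use post-baseline assessments only, with Day 1 serving as baseline. Add post-baseline to the 11.2.5.3 inclusion rule.
- The general period definitions in 9.1.1 need not change.

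The cost is a few sentences and a programming filter, with no new data. The Years 2 to 5 SAP (Introduction) records that the Week 52 outputs have already been produced. The practical step is therefore to check how Day 1 and the inclusion rule were programmed, then footnote or rerun the C-SSRS displays and the suicidality row of Table 2.06 if they differ.
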